3.3. Strata and Covariates

This study does not use a stratified randomization schedule when enrolling subjects. No covariates will be included in efficacy [and safety] analyses.

3.4. Examination of Subject Subgroups

There are no prespecified participant subgroupings for efficacy and safety analyses.

3.5. Multiple Comparison

Adjustments for multiplicity will not be made, because no formal statistical testing will be performed in this study.

3.6. Missing Data and Outliers

3.6.1. Missing Data

In general, missing data will not be imputed unless methods for handling missing data are specified.

For missing last dosing date of study drug, imputation rules are described in Section 4.2.1. The handling of missing or incomplete dates for AE onset is described in Section 7.1.5.2, and for prior and concomitant medications in Section 7.4.2.

3.6.2. Outliers

Outliers will be identified during the data management and data analysis process, but no sensitivity analyses will be conducted. All data will be included in the data analysis.

3.7. Data Handling Conventions and Transformations

The following conventions will be used for the imputation of date of birth when it is partially missing or not collected:

- If only month and year of birth is collected, then “15” will be imputed as the day of birth
- If only year of birth is collected, then “01 July” will be imputed as the day and month of birth
- If year of birth is missing, then date of birth will not be imputed

In general, age collected at Day 1 (in years) will be used for analyses and presented in listings. If age at Day 1 is not available for a subject, then age derived based on date of birth and the Day 1 visit date will be used instead. If an enrolled subject was not dosed with any study drug, the enrollment date will be used instead of the Day 1 visit date. For screen failures, the date the first informed consent was signed will be used for the age derivation. Age required for longitudinal and temporal calculations and analyses (eg, estimates of creatinine clearance, age at date of AE) will be based on age derived from date of birth and the date of the measurement or event, unless otherwise specified

Non-PK data that are continuous in nature but are less than the lower limit of quantitation (LOQ) or above the upper LOQ will be imputed as follows:

- A value that is 1 unit less than the LOQ will be used to calculate descriptive statistics if the datum is reported in the form of “< x” (where x is considered the LOQ). For example, if the values are reported as < 50 and < 5.0, values of 49 and 4.9, respectively, will be used to calculate summary statistics. An exception to this rule is any value reported as < 1 or < 0.1, etc. For values reported as < 1 or < 0.1, a value of 0.9 or 0.09, respectively, will be used to calculate summary statistics.
- A value that is 1 unit above the LOQ will be used to calculate descriptive statistics if the datum is reported in the form of “> x” (where x is considered the LOQ). Values with decimal points will follow the same logic as above.
- The LOQ will be used to calculate descriptive statistics if the datum is reported in the form of “≤ x” or “≥ x” (where x is considered the LOQ).

If methods based on the assumption that the data are normally distributed are not adequate, analyses may be performed on transformed data {or specify the transformation method, e.g., log-transformed data} or nonparametric analysis methods may be used, as appropriate.

CCI [REDACTED]

3.8. Analysis Visit Windows

3.8.1. Definition of Study Day

Study day will be calculated from the first dosing date of study drug and derived as follows:

- For postdose study days: Assessment Date – First Dosing Date + 1
- For days prior to the first dose: Assessment Date – First Dosing Date

Therefore, study day 1 is the day of first dose of study drug administration.

For subjects with intra-patient dose escalation per study protocol, days relative to first dose date under each dose level will be calculated and presented respectively in a listing of AEs for such subjects.

3.8.2. Analysis Visit Windows

The nominal visit as recorded on the CRF will be used when data are summarized by visit. Any data relating to unscheduled visits will not be assigned to a particular visit or time point.

However, the following exceptions will be made:

- An unscheduled visit prior to the first dosing of study drug may be included in the calculation of the baseline value, if applicable.
- Unscheduled visits after the first dosing of study drug will be included in determining the maximum postbaseline toxicity grade.
- For subjects who prematurely discontinue from the study treatment, the EOT visit data will be assigned to what would have been the next scheduled visit where the respective data were scheduled to be collected.

3.8.3. Selection of Data in the Event of Multiple Records in an Analysis Visit Window

Depending on the statistical analysis method, single values may be required for each analysis window. For example, change from baseline by visit usually requires a single value, whereas a time-to-event analysis would not require 1 value per analysis window.

If multiple valid, nonmissing measurements exist in an analysis window, records will be chosen based on the following rules if a single value is needed:

- For baseline, the last nonmissing value on or prior to the first dosing date of study drug will be selected, unless specified differently. If there are multiple records with the same time or no time recorded on the same day, the baseline value will be the average of the measurements for continuous data, or the measurement with the lowest severity (eg, normal will be selected over abnormal for safety electrocardiogram [ECG] findings) for categorical data.
- For postbaseline values:
 - The record closest to the nominal day for that visit will be selected.
 - If there are 2 records that are equidistant from the nominal day, the later record will be selected.
 - If there is more than 1 record on the selected day, the average will be taken for continuous data and the worse severity will be taken for categorical data, unless otherwise specified.

4. SUBJECT DISPOSITION

4.1. Subject Enrollment and Disposition

A summary of subject enrollment will be provided by cohort for each country and overall based on all enrolled subjects. The summary will present the number and percentage of subjects enrolled. For each column, the denominator for the percentage calculation will be the total number of subjects analyzed for that column.

A summary of subject disposition will be provided by cohort based on All Screened Subjects. This summary will present the number and percentage of subjects in the following categories:

- Screened Subjects
- All Enrolled Subjects
- Safety Analysis Set
- PK Analysis Set
- DLT-Evaluable Analysis Set
- Study Drug Completion Status
 - Completed Study Drug
 - Discontinued Study Drug
- Reasons for Discontinuation of Study Drug
- Study Completion Status
 - Completed Duration of Study
 - Discontinued Study
- Reasons for Discontinuation of Study

For the status of study completion and reasons for discontinuation, the number and percentage of subjects in each category will be provided. The denominator for the percentage calculation will be the total number of subjects in the All Enrolled Analysis Set corresponding to that column.

The following by-subject listings will be provided by cohort and subject identification (ID) number in ascending order to support the above summary table:

- Reasons for study drug or study discontinuation.

4.2. Extent of Study Drug Exposure and Adherence

Extent of exposure to study drug (GS-4224) will be examined by assessing the total duration of exposure to study drug GS-4224, the actual duration of exposure to GS-4224, and prescribed adherence to study drug. The summaries will be based the Safety Analysis Set.

4.2.1. Extent of Exposure to Study Drug

Total duration of exposure to study drug GS-4224 will be defined as last dosing date of study drug minus first dosing date plus 1, regardless of any temporary interruptions in study drug administration, and will be expressed in weeks using up to 1 decimal place (eg, 4.5 weeks). If the last study drug dosing date is missing,

- If the study drug is permanently withdrawn, the latest date among the study drug end date, clinical visit date, laboratory sample collection date, and vital signs assessment date that occurred during the on-treatment period will be used for subjects included in the final analyses or the last available date in the database snapshot for subjects who were still on treatment at the time of an interim analysis.
- If the study drug completion status is unknown, the earlier of the date of death or data cut-off date for analysis will be used.

The actual duration of exposure to GS-4224 during the DLT assessment window is defined as the last dosing date minus first dosing date plus 1 within the DLT assessment window (first 21 days of study drug dosing), taking into account investigator-prescribed dose interruptions in study drug administration within the DLT assessment window. The level of prescribed adherence to the study drug GS-4224 during the DLT assessment window will be determined by the actual duration of exposure to GS-4224 relative to the total duration of exposure specified by study protocol during a subject's DLT assessment window.

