### **8.7.1. Extent of Exposure**

A subject's extent of exposure to study drug data will be generated from the study drug administration data. Descriptive information will be provided by cohort, indication and treatment regarding the number of doses of study drug prescribed, the total number of doses taken, the duration of exposure to study drug, and the number and timing of prescribed dose interruptions.

GS-4224 compliance will be described in terms of the proportion of study drug actually taken based on returned pill count relative to the amount that was dispensed (taking into account physician-prescribed interruptions).

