3.1.4. DLT-Evaluable Analysis Set

The DLT-Evaluable Analysis Set includes all subjects in the Safety Analysis Set who enroll to the dose escalation cohort (excluding the Dose Escalation Biopsy Substudy), complete $\geq 75\%$ of the prescribed study treatment (ie., at least 16 of 21 doses) and have safety assessments through the protocol specified DLT assessment window (first 21 days of study dosing, inclusive) or have experienced a DLT prior to the completion of first 21 days of study dosing. Safety assessment relevant to the DLT-Evaluable Analysis Set definition will include laboratory serum chemistry tests and hematology tests as specified in the protocol. Determination of the MTD will be based on the DLT-Evaluable Analysis Set.

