4.2.2. Adherence to Study Drug

The level of prescribed adherence during the DLT assessment window will be expressed as a percentage using the following formula:

Prescribed Adherence During DLT Assessment Window (%) =

$$= \frac{\text{Actual Duration of Exposure to Study Drug During DLT Assessment Window}}{\text{Total Duration of Exposure Specified by Protocol During DLT Assessment Window}} \times 100$$

Descriptive statistics for the level of prescribed adherence with the number and percentage of subjects belonging to adherence categories (eg, < 75%, ≥ 75%) will be provided by cohort for the Safety Analysis Set.

A by-subject listing of study drug (GS-4224) administration will be provided by cohort and subject ID number (in ascending order), including dosing date, total duration of exposure to GS-4224, actual duration of exposure, the prescribed adherence during the DLT assessment window, and reason for dose interruption.

The total duration of exposure to study drug will be summarized using descriptive statistics and using the number (ie, cumulative counts) and percentage of subjects exposed through the following time periods: 1 day, 3 weeks, 6 weeks, 9 weeks, 12 weeks, 18 weeks, and 24 weeks. Summaries will be provided by cohort for the Safety Analysis Set.

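### DLT-window adherence in the SAP is a date span, not a dose count, so a subject who took about half the doses can be reported as 100% adherent

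*SAP*

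**What the plan says.** SAP Section 4.2.1 gives the numerator: the actual duration of exposure in the window "is defined as the last dosing date minus first dosing date plus 1 within the DLT assessment window". The only adjustment that this section states for it comes from "taking into account investigator-prescribed dose interruptions in study drug administration within the DLT assessment window". The window is the "first 21 days of study drug dosing". Prescribed adherence is then "determined by the actual duration of exposure to GS-4224 relative to the total duration of exposure specified by study protocol" in that window, and Section 4.2.2 writes this as a percentage.

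Section 4.2.2 plans "Descriptive statistics for the level of prescribed adherence with the number and percentage of subjects belonging to adherence categories", giving below 75% and at or above 75% as the example split, for each cohort among treated subjects. It also plans a by-subject listing of drug administration with dosing dates and reasons for interruption.

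Three other places bear on the same quantity:

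- Protocol Section 8.7.1 promises the number of doses prescribed and the total taken. It bases compliance on drug actually taken, "based on returned pill count relative to the amount that was dispensed (taking into account physician-prescribed interruptions").
- SAP Section 3.1.4 requires, for a subject without a DLT, at least 75% "of the prescribed study treatment (ie., at least 16 of 21 doses"). Protocol Section 4.1.2 uses the same dose count for replacement.
- SAP Section 7.7 states that the protocol-specified safety analyses are unchanged.

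**The concern.** The quantity carries the name adherence and sits under the heading on adherence to study drug, but no term in it counts doses. Between the first and last dosing dates, only a prescribed interruption lowers it. A subject who forgets or declines doses mid-window looks fully adherent, and a twice-daily day with one dose taken counts as a full day.

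The 75% cut is the same as in the DLT-evaluability rule, so readers of the report will take the table as evidence that subjects received enough drug for the DLT assessment to be informative. The table can place a subject at or above 75% who fails the dose-count rule in SAP Section 3.1.4. The protocol's own compliance measure, which would show the gap, does not appear in SAP Section 4.2.

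**Working it through.** **Inputs.** The window is 21 days (SAP 4.2.1), taken here as the protocol-specified duration in the denominator. The first dosing date is Day 1 (SAP 3.8.1). Scheduled doses are 21 once daily or 2 × 21 = 42 twice daily (protocol 3.3). The cut is 75%.

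**The plan's own figure.** 0.75 × 21 = 15.75, so 16 doses are needed: 16/21 = 76.2% and 15/21 = 71.4%. The stated 16 of 21 is reproduced for once-daily dosing. It does not carry over to twice-daily dosing: 0.75 × 42 = 31.5, so 32 doses are needed, while 16/42 = 38.1%.

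**Formulas.** SAP adherence = (last dosing day − first dosing day + 1 − prescribed interruption days) / 21. Dose-based adherence = doses taken / doses scheduled.

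| Pattern in Days 1-21 | SAP figure | Doses taken / scheduled |
|---|---|---|
| Once daily, Days 1-10 and 21 | (21−1+1)/21 = 100% | 11/21 = 52.4% |
| Once daily, Days 1-5 and 17-21 | 100% | 10/21 = 47.6% |
| Once daily, Days 1 and 21 only | 100% | 2/21 = 9.5% |
| Twice daily, one dose every day | 100% | 21/42 = 50.0% |
| Once daily, stops after Day 10 | 10/21 = 47.6% | 10/21 = 47.6% |
| Once daily, misses Days 16-21 | 15/21 = 71.4% | 15/21 = 71.4% |
| Once daily, 6-day prescribed hold mid-window | (21−6)/21 = 71.4% | 15/21 = 71.4% |

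The first four rows are wrong and the last three are right. The ranking can also reverse: the subject who follows a six-day prescribed hold falls below 75%, while the one who skips ten mid-window days unprompted is shown at 100%.

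**How often this could matter.** The documents give no missed-dose rate, so this is an illustration under an assumption: once-daily dosing, Day 1 taken, and each later dose taken independently with probability p. The SAP figure reaches 75% if at least one dose is taken on Days 16-21, which has probability 1 − (1−p)^6. The dose rule is met if at least 15 of the other 20 doses are taken. Anyone meeting the dose rule also reaches 75% on the SAP figure, because 16 daily doses need 16 days. The chance of being shown at or above 75% with fewer than 16 doses is therefore the difference:

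| p | SAP figure ≥ 75% | At least 16 of 21 doses | Difference |
|---|---|---|---|
| 0.6 | 99.6% | 12.6% | 87.0% |
| 0.7 | 99.9% | 41.6% | 58.3% |
| 0.8 | 100.0% | 80.4% | 19.6% |
| 0.9 | 100.0% | 98.9% | 1.1% |

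**Against the protocol.** Section 8.7.1 needs a count of doses taken and a pill count. SAP Section 4.2 has neither as a summary. SAP Sections 2.1.2 and 2.1.3 name the analyses dropped after early termination, and this is not among them.

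**The case against.** The SAP calls the quantity prescribed adherence and defines it openly. Protocol Section 8.7.1 describes compliance overall, not in the DLT window. The measure does respond to early stopping, to misses at the end of the window and to prescribed holds. It is not the only relevant output: the listing in Section 4.2.2 shows dosing dates, the disposition table in Section 4.1 counts the DLT-Evaluable Set, and plasma concentrations are reported. The study ended in Phase 1b and the SAP serves a synoptic report. The examples are constructed, and at 90% daily intake the misclassification is about 1%. The documents do not show that dose-level diary data reach the database.

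Most of this limits the size of the point without removing it. The label would be an answer if a compliance measure stood beside this one, but none does. The listing may let a careful reader see gaps, yet the summary table would still be wrong.

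Two stronger readings should be resisted. A reader might infer that missed doses never count; the last rows of the first table show that they do when they move the last dosing date. A reader might also infer that under-dosed subjects enter the MTD assessment as DLT-free. SAP Section 3.1.4 defines that set by a dose count of its own, and no passage assigns it from the adherence variable. The once-daily subject with 11 doses fails that rule.

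**Conclusion.** The point holds as a defect in a descriptive safety summary. Followed exactly, SAP Sections 4.2.1-4.2.2 can report 100% adherence for a subject who took 52% (once daily) or 50% (twice daily) of scheduled doses. For doses that subjects miss on their own, the error is never downward. The table can disagree with the evaluability rule at the same 75% cut, and the SAP departs from protocol Section 8.7.1 without declaring it.

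No effect on the DLT-Evaluable Set or the MTD is shown. The shared cut-off invites using this variable to assign the set, but that remains a risk and not something the plan states. The conclusion assumes a 21-day denominator and no deduction beyond prescribed interruptions, as the text reads. How many subjects are affected is unknown, because it depends on a missed-dose rate that the documents do not give.

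**What to change.** - In SAP Sections 4.2.1-4.2.2, define DLT-window adherence as doses taken divided by doses scheduled on Days 1-21 for the assigned regimen: 21 once daily, 42 twice daily.
- Take doses from the dosing diary or pill counts. Protocol Appendix 2 schedules diary accountability at every Cycle 1 visit, and protocol Section 5.6 requires used and unused drug to be returned.
- Use this variable for the 75% table, so that it matches the 75% criterion in SAP Section 3.1.4. Keep the date span only as duration of exposure.
- Restore the compliance and doses-taken summaries of protocol Section 8.7.1, or declare the change in SAP Section 7.7.
- Reconcile the 16-of-21 wording in SAP Section 3.1.4 and protocol Section 4.1.2 with the twice-daily schedule.

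The cost is a change of wording and a small programming change, provided the dose counts are in the database, which should be confirmed first. Reported adherence may come out lower.

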4.2.2. Adherence to Study Drug

The level of prescribed adherence during the DLT assessment window will be expressed as a percentage using the following formula:

Prescribed Adherence During DLT Assessment Window (%) =

$$= \frac{\text{Actual Duration of Exposure to Study Drug During DLT Assessment Window}}{\text{Total Duration of Exposure Specified by Protocol During DLT Assessment Window}} \times 100$$

Descriptive statistics for the level of prescribed adherence with the number and percentage of subjects belonging to adherence categories (eg, < 75%, ≥ 75%) will be provided by cohort for the Safety Analysis Set.

A by-subject listing of study drug (GS-4224) administration will be provided by cohort and subject ID number (in ascending order), including dosing date, total duration of exposure to GS-4224, actual duration of exposure, the prescribed adherence during the DLT assessment window, and reason for dose interruption.

The total duration of exposure to study drug will be summarized using descriptive statistics and using the number (ie, cumulative counts) and percentage of subjects exposed through the following time periods: 1 day, 3 weeks, 6 weeks, 9 weeks, 12 weeks, 18 weeks, and 24 weeks. Summaries will be provided by cohort for the Safety Analysis Set.

4.3. Protocol Deviations

Subjects who did not meet the eligibility criteria for study entry, but enrolled in the study will be identified regardless of whether they were exempted by the sponsor or not. A by-subject listing will be provided for those subjects who did not meet at least 1 eligibility (inclusion or exclusion) criterion. The listing will present the eligibility criterion (or criteria if more than 1 deviation) that subjects did not meet and related comments, if collected.

Protocol deviations occurring after subjects entered the study are documented during routine monitoring. A by-subject listing will be provided for those subjects with important protocol deviation.

4.4. Assessment of COVID-19 Impact

This study was ongoing during the novel coronavirus (2019 nCoV [COVID-19]) pandemic, and the COVID-19 pandemic has caused a disruption in the regular visit schedules for this study. Some subjects were unable to attend onsite visits due to shelter in place guidelines, site closures, or other reasons. This section provides guidance on how to handle special situations due to COVID-19 in the analysis.

Adverse events (AEs) due to COVID-19 will be included in AE analyses if applicable. A by-subject listing of Adverse Events due to COVID-19 may be provided. The COVID-19

Standardized MedDRA Queries (SMQ) with Broad Scope in [Appendix 1](#) will be implemented.

4.4.1. Study Drug or Study Discontinuation Due to COVID-19

A by-subject listing of reasons for premature study drug or study discontinuation due to COVID-19 will be created.

4.4.2. Protocol Deviations Due to COVID-19

A by-subject listing will be provided for subjects with important protocol deviation related to COVID-19. A separate listing will be provided for subjects with non-important protocol deviation related to COVID-19.

4.4.3. Missed and Virtual Visits Due to COVID-19

A by-subject listing of subjects with missed or virtual visits due to COVID-19 will be provided by subject ID number in ascending order.

Information regarding virtual or missed visits due to COVID-19 was collected as free text in the CRF comment fields. The determination of missing or virtual visits due to COVID-19 was done using Natural Language Processing (NLP) to search the CRF comment fields. A detailed explanation of the algorithm is given in [Appendix 2](#).

